We will obtain epithelial cells from the lining of the nose using a technique called nasal brushing. This is a simple, nonsurgical procedure and is well tolerated by most people. We will gently brush the inside of the lateral wall of each nostril with a small, delicate, sterile brush. This procedure takes about 5 seconds for each nostril.

We also propose to correlate patterns of miRNA changes in our defined populations, with mRNA expression arrays. HMW RNA from isolated epithelial cells will be used for hybridization to Affymetrix HG-U133 Plus 2.0 microarrays. Images will be analyzed in the core facility and data will be normalized as follows: (1) per array, by dividing the raw data by the 50th percentile of all measurements; and (2) per gene, by dividing the raw data by the median expression level for all the genes across all arrays in a data set. We will determine whether up or down-regulated mRNAs are potential targets for previously identified miRNAs.

Phase II

Only subjects with Irritant asthma or Allergic asthma who have successfully completed the first phase of the study and have signed consent to be re-contacted will be recruited for the second phase of the study (Phase II). Phase II will involve two visits over a 2 week time period. For Phase II, we will first obtain sputum samples for a baseline analysis of cells. Study subjects will be provided with an inhaled corticosteroid, Fluticasone propionate HFA 220 mcg, 2 puffs twice a day (Treatment), or no treatment (No treatment). Fluticasone HFA will be provided by the study physician through the CTSI and the Bellevue Pharmacy. Treatment cases will be instructed to self administer the medication with a large volume spacer that will be provided to them. Inhaler teaching will be performed by study physician or coordinator at the time that the subject is provided the inhaler. Treatment Cases and No treatment controls will be provided a diary to record fluticasone inhaler. Treatment cases and No treatment controls will be allowed to use their usual rescue bronchodilator (albuterol) on an as needed basis. Treatment Cases and No treatment controls will return after 2 weeks for a repeat sputum induction.

2. Data Analysis and Data Monitoring:

We will start with 10 patients in each group to develop the basic techniques and measurements. Our group sample sizes of 10 and 10 achieve 80% power to detect a difference of 1.3 given the null hypothesis that the two-group difference is 0 and the estimated group standard deviations are 1.0 and 1.0, with a significance level (alpha) of 0.05 using a two- sided two-sample t-test. Based on results from these studies we will work with [name], our biostatistician and the NYU CI Genomics core for our statistical analysis. We put in a small number of patients as this is a pilot study to develop information that will allow for a subsequent appropriate power analysis.

For ENO and EBC analyses, we will express data as means \pm SD for normally distributed variables. For variables that are not normally distributed we will use medians and the interquartile range. We will use statistical analysis including unpaired *t* tests, Kruskal-Wallis test, and regression coefficients as appropriate. P values of < 0.05 will be considered significant. Differential expression of miRNA and hierarchical clustering will be performed with the genomics core. Statistics using *t* tests or algorithms designed specifically for data mining and biochip interpretation will be used. Pathway analyses will also be performed by the genomics computational core.

For Phase II, the primary outcome is the change in TSLP gene expression in epithelial cells after 2 weeks of treatment of inhaled corticosteroid compared to no treatment. We hypothesize that a significant reduction in the gene expression will be observed in the treatment group of inhaled corticosteroid compared with the untreated group. The difference between two randomized groups will be compared using the two-group *t*-test if data are normally distributed, and the nonparametric Wilcoxon test will be used for skewed data. The effect of inhaled corticosteroids on newly identified epithelial targets (gene expression array) will also be examined. This is an exploratory goal and will be performed after cell stabilization and short-term culture cells to insure appropriate RNA quality.

Sample size and power: Group sample sizes of 15 and 15 achieve 80% power to detect a difference of 1.3SD against the null hypothesis that both group means are equal with a significance level (alpha) of 0.01 using a two-sided two-sample *t*-test assuming equal variance.

3: Data Storage and Confidentiality:

Care will be taken to ensure confidentiality. Research records will be held in locked cabinets or secure storage rooms. All transmission of data to the coordinating center for analysis will be by study ID code only.

Sample specimens will be stored for up to 10 years for future use or until the end of the study. Participants will be able to decide if they want any of their specimens stored for research done at a later time.

IV. Risk/Benefit Assessment

1. Risk: Minimal Risk

Spirometry, ENO, IOS and EBC.

Participation in these studies will pose minimal risk of physical or psychological harm. Spirometry, impedance oscillometry, ENO and exhaled breath condensate collection are minimally invasive.

Methacholine testing: MCT has been performed with no serious side effects. Participants may develop transient side effects such as cough, mild dyspnea, and chest tightness although many experience no symptoms. Inhaled methacholine can cause bronchoconstriction and safety of each subject is considered prior to testing. A physician and the medical director of the pulmonary lab are trained to treat acute bronchospasm, including appropriate use of resuscitation equipment, and a physician is present during the procedure. Our pulmonary function lab in Bellevue Hospital is well trained in performing MCT in the clinical and research setting. If bronchospasm occurs appropriate medications will be administered as per the lab protocol (oxygen, nebulizers, subcutaneous epinephrine). If a participant in the study develops an acute asthma episode during any part of this procedure, the procedure will be stopped and albuterol will be administered to improve breathing. The bronchodilator will be provided by a physician involved in the study and the participant will be monitored until their breathing has returned to its baseline.

For all women of childbearing ability, a pregnancy test will be performed before the methacholine challenge study. Pregnant subjects will be excluded from the study.

Induced sputum: Sputum induction involves inhalation of hypertonic saline aerosol, a stimulus known to cause bronchoconstriction in asthmatic subjects. To ensure participant safety during sputum induction we will follow the following protocol: procedure will be performed in a hospital setting by highly trained and experienced staff, administration of a bronchodilator can be given to inhibit hypertonic saline-induced bronchoconstriction, we will limit the sputum induction to 20 minutes and monitor the participant's symptoms closely with repeat spirometry every 2 minutes after induction. If bronchoconstriction occurs we will follow the protocol discussed under MCT.

Nasal brushing: Nasal brushing. We do not anticipate any untoward risk of performing this procedure in normal individuals or in those with asthma. This procedure is not usually painful but some people experience a moment of discomfort for about 5 seconds during the brushing. There may be minor irritation such as reflex tearing from your eyes, or sneezing. There may be a rare chance that there is a small amount of bleeding as if you had a scrape. These possible discomforts resolve on their own.

Administration of inhaled corticosteroid –We are providing high dose inhaled corticosteroid (*Fluticasone propionate HFA 220 mcg*) for a short (2 week) period of time. This medication poses no more than minimal risk to research subjects and the risk is minimized by the short treatment period and the use of a large volume spacer. This is an approved treatment for asthma. The most common symptoms experienced by patients who have taken fluticasone are: upper respiratory infections (25-29%), hoarseness or dysphonia (1-4%), inflammation of throat, nose or sinuses (1-12%), oral candidiasis (2%) , nausea and vomiting (1%), other gastrointestinal symptoms (1-2%), and muscle or bone pain (3%). Subjects will be instructed to avoid oral candidiasis by rinsing their mouth after administration of the medication.

2. Protection against Risks:

All participants will be provided with a contact physician capable of providing sources of appropriate medical or professional intervention in the event of adverse effects to the subject. This person will be available on a 24 hour contact basis through the New York University/Bellevue Hospital Asthma Clinic hot line.

3: Potential Benefit to the Subjects:

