H#: 10-01191
NCT02740543

Title: Biomarkers of Irritant-Induced and Allergic Asthma – Phase I and Phase II

Principal Investigator: [name]
 Co-Investigator: [name]
 Professional Study Personnel: [name]
 [name]
 [name], MA
 [name]

Specific Aims

Asthma is a heterogeneous disease, and although much is understood about mechanisms of inflammation in allergic asthma, less is known about mechanisms of irritant-induced asthma (IA) (5, 7). Understanding the underlying similarities and differences in mechanisms of these two types of asthma will help focus current treatments and lead to development of new therapies. We have a longstanding NYU/Bellevue Asthma registry (NYUBAR), with a large population (N = 900) of asthma cases and controls, a program that has been housed at the CTSI (formerly GCRC). The destruction of the World Trade Center (WTC) resulted in massive dust, gas and fume exposures to local residents, workers and cleanup workers and individuals involved in rescue and recovery and adverse respiratory health effects of this disaster are reported more than 7 years after 9/11 (1-4). Many responders, as well as those exposed as residents or local workers, have developed IA, asthma that arises after a lag from an environmental exposure (1, 5, 6). The WTC Environmental Health Center (WTC EHC) is one of the three New York City (NYC) WTC Centers of Excellence and the only one that focuses on treatment and monitoring of local workers and residents. As such, it has a large population of individuals with irritant-induced asthma. We now propose to use participants from the NYUBAR and the WTC EHC to expand our knowledge of irritant and allergic asthma. Non-invasive studies allow for the assessment of airway inflammation, a non-specific response to environmental exposure and injury. Recent technologies also allow for assessment of microRNA (miRNA), small RNAs that regulate gene expression at the post-transcriptional level and thus serve as a pathway to regulation of inflammation. **We will test the hypothesis that airway inflammation in irritant and allergic asthma may be similar, but result from divergent miRNA regulatory pathways expressed in sputum cells.** These studies will provide preliminary data for future studies that will help identify biological pathways to categorize these asthma phenotypes and target future treatment interventions. We propose the following aims:

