Specific Aim 1: To test the hypothesis that irritant-induced asthma is characterized by elevated markers of inflammation in a manner similar to that described for allergic asthma.

SA1.a We will identify and phenotype individuals with WTC dust cloud-exposed irritant-induced asthma (IA), individuals with allergic asthma (AA) and healthy unexposed individuals (Controls).

SA1.b We will measure biomarkers of inflammation using noninvasive techniques for exhaled nitric oxide (ENO) and 8-isoprostanate from exhaled breath condensate (EBC) in WTC irritant-induced asthma (IA), individuals with allergic asthma (AA) and in healthy unexposed individuals (Controls).

SA1.c We will measure inflammatory cells in induced sputum from individuals with IA, AA and Controls.

Specific Aim 2: To test the hypothesis that the miRNA expression in airway epithelial cells will differ between IA, AA and Control individuals.

SA2.a. We will isolate RNA from epithelial cells and inflammatory cells in induced sputum and assess the miRNA expression profile using microarray technology among individuals with irritant-induced asthma (IA), individuals with allergic asthma (AA) and healthy unexposed individuals (Controls).

SA2.b. We will identify the mRNA targets of the differentially expressed miRNAs by using publicly available databases and correlate miRNA and mRNA expression.

Specific Aim 3: To test the hypothesis that levels of RNA of targets in human sputum cells will differ before and after the administration of inhaled corticosteroids in asthmatics (both IA, AA). The importance of this hypothesis in the characterization of irritant induced and allergic asthma is to further characterize the regulatory pathways expressed in sputum cells by identifying which inflammatory markers are steroid sensitive and steroid resistant.

SA3.a. We will isolate RNA targets in discrete sputum cells from induced sputum in IA and AA individuals and compare levels before and after administration of inhaled corticosteroids.

I. Background and Significance

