Asthma, a complex syndrome with many clinical phenotypes, is characterized by a variable degree of airflow obstruction, airway hyperresponsiveness, and airway inflammation which results in symptoms of cough, shortness of breath, wheezing and chest tightness (9). Asthma is a heterogeneous disease with some patients having a clear allergic component, whereas others non-allergic asthma, some of which arises after irritant exposure (dust, gas, vapors or fumes). In the WTC population there is a high prevalence of asthma-like symptoms that developed after 9/11 which are treated with typical asthma medications despite the uncertainty of the underlying mechanisms and pathophysiology. We know from individuals under treatment in the WTC EHC that respiratory symptoms continue to persist more than 5 years after the event and although most individuals with respiratory symptoms have normal screening spirometry, there is a high rate of airway hyperresponsiveness consistent with irritant-induced asthma (1, 10). The underlying pathology and inflammatory response in irritant-induced is unclear and may differ from classic allergic asthma. Little is known about mechanisms of irritant-induced asthma.

Why study non-invasive markers of inflammation

There are ongoing efforts to define biomarkers to characterize airway inflammation in asthma. Presently the “gold standard” to measure airway inflammation and biomarkers of inflammation in humans involves direct airway sampling by bronchoscopy (11). The invasive nature of bronchoscopy makes it impractical and thus there is much interest in implementation of noninvasive methods. Approaches using exhaled nitric oxide (ENO), exhaled breath condensate (EBC) and induced sputum (IS) as surrogates of the lung have many advantages including sampling simplicity, subject comfort, analytical ease and safety for longitudinal studies. Few studies have been performed on non-invasive markers of irritant-induced asthma. A recent report demonstrated a similar inflammatory cell profile of increased eosinophils and neutrophils in induced sputum in individuals with acute irritant-induced asthma from accidental inhalational injury compared to individuals with allergic occupational asthma (12).

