AA: These patients will be recruited from the NYUBAR (N = 30) and advertising and will have asthma as defined by NIH guidelines (51), persistent symptoms, and absence of WTC dust exposure.

Control: These patients will be recruited from the NYUBAR (N = 30) and advertising and will have no respiratory sx, no asthma diagnosis, no WTC dust exposure. Additional appropriate inclusion and exclusion criteria will be developed for each group including tobacco use, other lung disease, timing of inhaled corticosteroids etc.

The study will entail two to three visits. On visit 1 (V1) all individuals will sign informed consent to participate in the study under an NYU IRB approved protocol. A questionnaire will be completed with standardized questions that include information on WTC exposures, demographics, presence and severity of respiratory symptoms, tobacco history and past medical history. Individuals will undergo spirometry with inhaled bronchodilator. Individuals will undergo methacholine challenge test (visit 1a) if they have normal spirometry or no bronchial hyperresponsiveness. On visit 2, individuals will return to undergo ENO, EBC and spirometry with pre and post bronchodilator maneuvers and induced sputum. Blood will be obtained for CBC with differential cell count, and assessment of total IgE and allergen-specific IgE. Blood will also be stored for future analysis of inflammatory markers. Based on our experience, we have had individuals unable to produce enough sputum and thus yield too small a number of cells. These individuals are excluded from data analysis. In addition, we also have subjects who are able to produce sputum and return for repeat sputum testing.

SA1.b We will measure biomarkers of inflammation using noninvasive techniques for exhaled nitric oxide (ENO) and 8-isoprostanate from exhaled breath condensate (EBC) in WTC IA, AA and controls.

We will use the handheld NIOX MINO® to measure ENO (Aerocrine, Sweden) (17, 18, 20, 52). The NIOX MINO® fulfills the ATS recommendations and provides reliable readings and is portable and we have experience with it (53). Most healthy individuals have ENO levels in the range of 5-35 ppb (some variation with age, gender, race/ethnicity) (54). Individuals with asthma have ENO levels that can range from 25-80 ppb and even higher (18, 61, 62).

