1. Number of Subjects: 90 (this includes the total number of subjects enrolled in phase I and II of the study that are able to produce sputum)

[Number of subjects in Phase II: 40]

The estimated number of subjects to be enrolled (signed consent, including screen failures) is 300.
2. Gender of Subjects: Men and Women (50 % each)
3. Age of Subjects: 18-80 years of age
4. Racial and Ethnic Origin: The sample population of approximately 80 participants is expected to include a distribution of subjects by race/ethnicity in relation to our local population which includes a high percentage of minority subjects (36% White, 35% Black, 50% Hispanic)
5. Inclusion Criteria:

Inclusion for the WTC population with Irritant-Induced Asthma (IA):

Patients will be recruited from the WTC EHC and will have WTC dust cloud exposure, new symptoms after 9/11, and symptoms of wheeze and shortness of breath (> 2x / week) in the 4 weeks before inclusion (persistent symptoms). We will be recruiting new subjects for phase II of the study but participants who will have completed Phase I of the study and were able to produce adequate sputum samples may also be contacted for Phase II.

Inclusion for Allergic Asthma population(AA): Patients will be recruited from the NYUBAR or advertisement and will have asthma as defined by NIH guidelines, persistent symptoms, absence of WTC dust exposure. Participants who will have completed the Phase I of the study and were able to produce adequate sputum samples may also be contacted for Phase II.

Inclusion of Control Population: Patients will be recruited from the NYUBAR and will have no respiratory symptoms, no asthma diagnosis, no WTC dust exposure, no current tobacco use, ≤ 5 p-y history of tobacco use, and normal spirometry with no bronchodilator response and negative methacholine challenge in past 6 months.

Additional inclusion criteria for individuals with IA and AA: ≥ 18 years of age, current nonsmoker, ≤ 5 pack year (p-y) history of tobacco use, spirometry in the past 6 months or on day of evaluation with a bronchodilator response of $\geq 12\%$ and 200 ml improvement in FEV₁ or a positive methacholine challenge test (decrease in FEV₁ $\geq 20\%$ (PC20) after inhalation of ≤ 16 mg/ml of methacholine), inhaled corticosteroid use in previous 1 month or more will be allowed.

Inclusion criteria for Phase II

Successfully completed Phase I

Has asthma according to Phase I diagnostic criteria

Signed consent to be re-contacted

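### The allergic asthma group needs no evidence of allergy and no rule uses the planned IgE, so IA versus AA cannot by itself support an irritant-versus-allergic conclusion

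*Combined protocol and SAP*

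**What the plan says.** The AA group is defined twice. Research Design and Methods, SA1.a, asks for "asthma as defined by NIH guidelines (51), persistent symptoms, and absence of WTC dust exposure". Section II, item 5 (Inclusion Criteria) repeats the same three elements: "asthma as defined by NIH guidelines, persistent symptoms, absence of WTC dust exposure". The further criteria that item 5 sets for both asthma groups concern age, smoking, bronchodilator or methacholine response, and inhaled steroid use. Neither these nor the exclusions in item 6 mention an allergy history, a skin test or an IgE result. SA1.a does say that "Additional appropriate inclusion and exclusion criteria will be developed for each group", but its examples are tobacco, other lung disease and steroid timing.

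IA is defined by WTC dust cloud exposure, symptoms that began after 9/11, and persistent wheeze and breathlessness. This agrees with the Specific Aims, which describe it as "asthma that arises after a lag from an environmental exposure".

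SA1.a plans blood at visit 2 for "assessment of total IgE and allergen-specific IgE". No section names an allergen panel, a cut-off, a classification or an analysis that uses the result. Statistical Analysis and section III.2 do not mention IgE.

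The Background (Why study irritant-induced asthma) says that some patients have an allergic component and "others non-allergic asthma, some of which arises after irritant exposure (dust, gas, vapors or fumes". The central hypothesis is that "airway inflammation in irritant and allergic asthma may be similar, but result from divergent miRNA regulatory pathways expressed in sputum cells". Specific Aim 1 looks for "elevated markers of inflammation in a manner similar to that described for allergic asthma". SA2.a and Anticipated results plan a direct comparison of IA with AA, in the latter section after pooled asthma has been compared with controls.

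**The concern.** A person with non-allergic asthma and no WTC dust exposure meets every AA criterion as written, and the Background says that such asthma exists. What separates the two asthma groups is exposure and time of onset. Allergy plays no part. Yet the hypothesis, the aims and the group label all speak of allergic asthma.

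At stake is the interpretation of one contrast. If some AA patients are non-allergic, neither a similarity nor a difference between IA and AA in inflammation markers or miRNA can be read directly as a statement about irritant versus allergic mechanisms. The information that could narrow the gap is already due to be collected.

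**Working it through.** **1. Definitions side by side.**

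| Element | IA | AA |
|---|---|---|
| WTC dust | dust cloud exposure required | must be absent |
| Onset | after 9/11 | not specified |
| Persistent symptoms | required | required |
| Bronchodilator or methacholine response | required | required |
| Evidence of allergy | not used | not used |
| Recruitment source | WTC EHC | NYUBAR or advertising |

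The rows that differ are exposure, onset and source. The allergy row is the same in both columns.

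**2. The plan's own power figure.** Statistical Analysis states 90% power for a difference of 0.73 with 50 per group, SD 1.0 and two-sided alpha 0.05. For a two-sample t test the noncentrality is 0.73 / sqrt(1/50 + 1/50) = 3.65 on 98 degrees of freedom, which gives 95.1%. The stated 90% does not reproduce. That is a separate matter and nothing below depends on it. The same section aims for 30 evaluable per group (50 × 38/65 = 29.2). At 30 per group the noncentrality is 0.73 / sqrt(2/30) = 2.83 on 58 degrees of freedom, and power is 79.4%.

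**3. Illustration of what non-allergic AA patients could do.** Inputs from the plan: 0.73 SD (a generic figure, not tied to IA versus AA), SD 1.0, two-sided alpha 0.05, 30 per group. Assumed inputs: the non-allergic share f of AA, and the mean difference k between non-allergic AA and IA. The documents give neither. The expected difference is (1 − f) × 0.73 + f × k.

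At f = 20%:
- k = 0 (they resemble IA): 0.8 × 0.73 = 0.584 SD, power 60%. Allowing for the wider mixture SD in AA, power is 59%.
- k = 0.73 (they resemble allergic AA): 0.73 SD, power 79%, no change.
- k = 1.46 (twice as far from IA): 0.584 + 0.292 = 0.876 SD, an overstatement.

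For f from 10% to 40%, k = 0 gives 0.66 to 0.44 SD and power of 71% to 39%, while k = 1.46 gives 0.80 to 1.02 SD. The sign of the distortion depends wholly on k.

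**4. Cost of restricting AA to IgE-positive patients.** At an assumed 20% IgE-negative, 24 of 30 AA remain against 30 IA. The noncentrality is 0.73 / sqrt(1/24 + 1/30) = 2.67 on 52 degrees of freedom, and power is 74%. The 95% CI half-width is 2.007 × sqrt(1/24 + 1/30) = 0.55 SD. At 30 per group it is 2.002 × sqrt(2/30) = 0.52 SD. For 10% to 40% IgE-negative, power runs from 77% to 67% and the half-width from 0.53 to 0.60 SD.

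**The case against.** The strongest reply is that the intent to establish allergy is present. SA1.a commits to phenotyping allergic asthma and lists IgE under that sub-aim, Preliminary data describes registry members as phenotyped, and Statistical Analysis allows regression. What is missing may be only a cut-off. Part of this stands: the guideline and the registry's phenotyping were not available for review. But no section says that allergy status in the registry is known or used, AA may also come from advertising, and regression is mentioned without any covariate.

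A second reply is that IgE in AA alone would not isolate the contrast, since IA patients may also be sensitised and AA excludes only WTC dust. Anticipated results itself suspects that other, more prolonged exposures cause irritant asthma. This stands, and it shapes the fix.

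A third is that some analysis has already been done: SA1.c, Statistical Analysis and Anticipated results describe samples processed and a publication. This also stands. A rule set now comes before the final analysis only.

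A fourth is that the non-allergic share and its position are assumed, so the figures measure nothing about this trial. That is right, and they are offered only as illustration.

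A reader might go further in three ways that the documents do not support:
- That IA versus AA is biased towards no difference. This needs non-allergic AA to resemble IA, which nothing in the documents shows.
- That sensitised IA patients are misclassified. IA is defined by exposure and onset, so they are not.
- That the whole study is undermined. Most comparisons do not depend on AA being allergic.

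**Conclusion.** The point holds as a gap between the label and the definition. As written, IA versus AA compares WTC-exposed asthma with onset after 9/11 against WTC-unexposed asthma. By itself it cannot support the irritant-versus-allergic conclusion in the Specific Aims. Confidence in the missing criterion is high, subject to one assumption: that the cited guideline's definition of asthma does not require allergy.

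The consequence is much less certain. The direction and size of any distortion are unknown; under the assumed inputs it ranges from dilution through no effect to overstatement. Pooled asthma versus control, IA versus control, and treatment versus no treatment in Phase II are not affected. The gap should be closed, because the contrast is central to the hypothesis and the IgE measurement is already planned.

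**What to change.** Before the final IA versus AA analysis, and with a statement that earlier samples have already been analysed and published:

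- Fix the allergen panel and the IgE positivity cut-off, and apply the same rule to AA and IA. As scheduled, IgE is drawn at the same visit as the biomarkers, so it would classify patients for analysis and not screen entry.
- Report IA versus AA for all AA as enrolled and for IgE-positive AA, each as an estimate with a 95% confidence interval.
- Tabulate IgE status in IA and in the subjects used for the arrays. Treat any contrast split by IgE status within IA as exploratory.
- Use the label 'allergic' only for the IgE-positive AA set.
- State that IgE shows sensitisation and not mechanism, that AA excludes WTC dust but no other irritant exposure, and that exposure and recruitment source remain confounded.
- Where IgE results are missing, or if the rule is not adopted, call the group 'WTC-unexposed asthma' and limit the conclusion to that.

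This needs no new test and no extra enrolment, but the restricted contrast has fewer AA patients and is less precise: with 24 of 30 remaining, power for 0.73 SD is 74% instead of 79%. Keeping 30 IgE-positive AA would not be free. At the same assumed 20% IgE-negative it needs 30/0.8 = 37.5, so 38 evaluable AA, which is 65 accrued at the plan's sputum yield of 38/65. Relabelling alone needs no data but gives up the irritant-versus-allergic claim.
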